### 1. OBJECTIVES

1. **PRIMARY OBJECTIVE:** To assess the effect of absorbable anchor compared to suturing for mesh attachment to vagina in robotic assisted sacrocolopexy on the length of surgery for this portion of the procedure.
2. **SECONDARY OBJECTIVES:**
  - i. To assess intraoperative and
  - ii. postoperative complication rates,
  - iii. Intraoperative 10 cm visual analog scale (VAS), to subjectively assess surgeon satisfaction with the technique
  - iv. post-operative Pelvic Organ Prolapse Quantification (POPQ) evaluation for anatomic failure and
  - v. a VAS of the vaginal walls overall appearance
2. **HYPOTHESES** For women undergoing sacrocolpopexy surgery at a large managed care organization:
  1. **PRIMARY HYPOTHESIS:** Attachment of the mesh to the vagina with absorbable anchors compared to standard treatment (suturing) will require 50% shorter surgical time for the mesh attachment portion of the procedure.
  2. **SECONDARY HYPOTHESIS:** Anchor suture staples compared to standard treatment will:
    - i. have similar rates of intra-operative and post-operative complications
    - ii. have similar rates of surgical failure
    - iii. not have different appearance on the VAS of the vaginal walls
    - iv. elicit higher reported satisfaction from surgeons
3. **BACKGROUND**
  1. **PELVIC ORGAN PROLAPSE:** Pelvic organ prolapse (POP) is the descent of one or more of four different anatomic structures: a) the uterus (cervix), b) the apex of the vagina (in those status post-hysterectomy) c) the anterior vaginal wall, or d) the posterior vaginal wall. It is caused by chronic intra-abdominal pressure on weakened pelvic organ supports. An estimated 41.1% of women aged 50-79 have some degree of prolapse on exam [1,2], while only 2.9-8% of all adult women report symptomatic prolapse symptoms [3-5]. Severity of POP is defined by the Pelvic Organ Prolapse Quantification (POPQ) system [6]. Risk factors include age, childbirth (especially vaginal and operative vaginal deliveries), white race, family history, constipation, obesity, smoking, and menopause. Symptoms can include a vaginal bulge, pressure, or discomfort.

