## 2. ASSESSMENTS

### i. STUDY SCHEDULE

The timing of study is summarized in the Study Schedule.

	Screening	Surgery	Post-Operative Visits	
Visit	1	1	1	2
Month	Pre-op	0	1.5	6
Informed consent	X			
Demographics	X			
Pregnancy	X			
Efficacy				
POPQ	X		X	X
Procedure length		X		
Surgeon+Fellow Satisfaction (VAS)		X		
PGI-I			X	X

PFDI 20	X			
Safety				
Vaginal Wall Appearance (VAS)			X	X
Adverse events		X	X	X
Patient VAS for Pain			X	X

ii. **POP DIAGNOSIS/BASELINE POPQ:** During the preoperative visit for evaluation of POP, the provider (nurse practitioner, resident, fellow, and/or attending) will perform a POPQ exam. Each component, Aa(midline anterior vaginal wall, 3cm above external urethral meatus), Ba(most distal point of the anterior vaginal wall from the vaginal cuff or cervix, C(most distal edge of the cervix or cuff), GH(the distance from the middle of the external urethral meatus to posterior hymen), PB(posterior margin of the genital hiatus to midanal opening), tvl(greatest depth of the vagina, Ap(midline posterior vaginal wall, 3cm proximal to the hymen), Bp(the most distal point of the posterior vaginal wall from the vaginal cuff or cervix), D(posterior fornix) will be assessed. Patient will be diagnosed with POP, defined as the descent of one or more of four different anatomic structures, a) the uterus(cervix), b)the apex of the vagina (in those status post hysterectomy) c) the anterior vaginal wall, or d) the posterior vaginal wall. This is defined on exam as the POPQ points Ba, C, or Bp >0 cm beyond the hymen. In addition, uterine (Cervix) descent into at least the lower half of the vagina (defined as point C>-TVL/2) or post hysterectomy vault into the lower 2/3 of the vagina, Bothersome bulge symptoms as indicated on question 3 of the PFDI-20 form relating to 'sensation of bulging' or 'something falling out,' and desires surgical treatment for uterovaginal or vault prolapse undergoing minimally invasive SCP.

iii. **BASELINE DEMOGRAPHICS:** Patient baseline demographic information will be assessed from the electronic medical record. Information on age, BMI, ethnicity, co-morbidities, and allergies will be obtained.

iv. **INTRAOPERATIVE:** The following will be tracked: intraoperative adverse events, total surgical time, sacrocolpopexy time, mesh attachment time, type of mesh, number of attachment points

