ii. **SECONDARY OUTCOME MEASURE:** Our secondary efficacy objectives include: 1) VAS of the operating surgeon subjective technique satisfaction assessment 2) post-operative POPQ, mesh erosion anatomic assessment, palpable anchor assessment and 3) VAS of the vaginal walls general appearance. The latter two will be recorded by the provider who is blinded at 6 weeks and 6 months, who will perform POP-Q as well as the VAS assessment of the walls of the vagina's general appearance. Surgical failure of a patient is if the points on POP-Q, if  $B_p, B_a \geq 0$  cm, or  $C > - \frac{1}{2}$  TVL. The VAS will have four components, global satisfaction, apex, anterior wall, and posterior wall. The instructions for all four VAS will be as follows: "Please designate a "X" at the VAS that rates closest your sacrocolpopexy evaluation." The anterior compartment assessment at the VAS left side will say "the vaginal mesh at the ANTERIOR seems to lay level without folding or bunching." At the other VAS side the text will say "mesh at the vaginal ANTERIOR is completely folded and bunched." Comparable phrasing will be used on the for posterior and apical compartment VAS. For the global satisfaction VAS, the side on the left it will say "I will use this suture routinely; as it meets my needs for attachment of mesh" and text at the other VAS end will say "I do appreciate the results, I will not use this attachment technique in my practice;"

iii. **SAFETY AND TOXICITY MEASURES:** Safety will be assessed as several points throughout the study. During the admission for surgical care, safety measures and complications will be assessed. During the surgery and admission, complications, including but not limited to hemorrhage, bleeding, nerve injury, infection, urinary retention, bowel injury, bladder/urethral injury will be assessed. Post-operatively at the 6 week, and month visit (along with query of electronic medical record for additional ER and ambulatory visits) additional safety measures will be assessed. At the standardized postoperative visits mesh exposure and erosion will be assessed. In addition pain and reoperation for pain or mesh erosion and exposure will be assessed.

4. **MONITORING AND ETHICAL CONSIDERATIONS:** To safeguard complete, reliable and accurate data, the principal investigator will:
  - i. provide preliminary and follow up training to study coordinators and providers on research procedure, participant recruitment, and completion of outcome reports

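### The vaginal-wall appearance VAS is worded to rate how the mesh lies and whether the rater would use the technique, so it does not directly measure the outcome in secondary hypothesis iii

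*Protocol*

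**What the plan says.** Protocol section 2.2 states as secondary hypothesis iii that the anchor arm will "not have different appearance on the VAS of the vaginal walls". Section 5.3.ii lists the wall-appearance VAS as the third secondary measure and says of the second and third measures: "The latter two will be recorded by the provider who is blinded at 6 weeks and 6 months". The study schedule (5.2.i) agrees: the row beginning "Vaginal Wall Appearance (VAS" is marked at the two postoperative visits and not at surgery. Section 5.2.vi requires that the postoperative examiner is not the provider who operated.

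Section 5.3.ii then gives the VAS four components: global satisfaction, apex, anterior wall and posterior wall.

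- **Anterior:** from "the vaginal mesh at the ANTERIOR seems to lay level without folding or bunching" to "mesh at the vaginal ANTERIOR is completely folded and bunched".
- **Posterior and apex:** "Comparable phrasing will be used on the for posterior and apical compartment VAS".
- **Global:** the left end reads "I will use this suture routinely; as it meets my needs for attachment of mesh". The right end says that the rater would not use the technique in practice.

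Section 5.3.iii treats visible mesh separately, as a safety finding: "At the standardized postoperative visits mesh exposure and erosion will be assessed". Neither Protocol section 6.3 nor SAP section 1.3 names this VAS. It falls under the general provision of a t-test or Mann-Whitney test for continuous variables, and no margin is set.

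**The concern.** The name of the outcome and the content of the form do not match. The outcome is how the vaginal wall looks. The compartment scales ask how the mesh lies, and the global scale asks about adopting a technique.

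The rater is also ill suited to the questions. Sections 3.4 and 4.1 place the mesh on the fibromuscular layer of the vagina, so an examiner at a clinic visit presumably judges its lie indirectly, by contour or by touch, unless it is exposed. That is an inference; the documents do not say how it is to be judged. The global item asks the examiner to endorse or reject a method of attachment to which that examiner is masked.

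At stake is the reading of hypothesis iii. Because the hypothesis is one of no difference, anything that makes the scale less informative works in its favour. A non-significant result could be reported as evidence that anchors leave the vaginal wall looking the same as sutures do, when the form never asked that question.

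**Working it through.** **Step 1. Each item against the outcome it is meant to measure**

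| Item | What the end labels rate | Rater and time (5.3.ii, 5.2.i) | Names the wall's appearance? |
|---|---|---|---|
| Anterior | Lie of the mesh | Blinded examiner, 6 weeks and 6 months | No |
| Posterior | Lie of the mesh (comparable phrasing; labels not printed) | Same | No |
| Apex | Lie of the mesh (comparable phrasing; labels not printed) | Same | No |
| Global | Willingness to use the technique | Same, on a plain reading | No |

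Four items at two visits give 4 × 2 = 8 scores per patient. Of these, 3 × 2 = 6 rate mesh lie, 1 × 2 = 2 rate the technique, and none is worded on the wall.

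**Step 2. Does anything elsewhere supply the missing link?**

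- Section 4.5 has the examiner look for palpable suture and anchors, and 5.3.ii lists palpable anchors. Neither mentions palpating mesh for folds.
- Section 5.3.i has a validation paragraph for the timing outcome. There is none for this VAS, and no plan to check rater agreement.
- Section 5.4.i promises training in completing outcome reports but does not say how mesh lie is to be judged.

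**Step 3. The plan's own sample size, which also limits the VAS**

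Inputs (Protocol 6.4, SAP 1.4): 40 versus 20 minutes, SD 20, α = 0.05 (taken as two-sided), power 80%.

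- Standardised difference = (40 − 20)/20 = 1.0.
- Normal approximation: n = 2 × (1.960 + 0.842)² / 1.0² = 15.7, so 16 per arm.
- Two-sample t-test: 16.7, so 17 per arm, with power 80.7% at 17. This reproduces the stated figure.
- Dropout: 17/(1 − 0.30) = 24.3, so 25 per arm, as stated.

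**Step 4. What that size can show on the VAS (illustration)**

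The documents give no SD, expected difference or reliability for the VAS, so these are assumptions. With reliability r, a true standardised difference d is observed as d × √r, and the t-test has non-centrality d × √r × √(n/2).

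With r = 1, 80% power needs d = 0.99 at 17 per arm or 0.81 at 25 per arm. Below that, power is:

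| Assumed d | n per arm | r = 1.0 | r = 0.5 | r = 0.25 | r = 0.1 |
|---|---|---|---|---|---|
| 0.5 | 17 | 29.3% | 17.0% | 10.9% | 7.3% |
| 0.5 | 25 | 41.0% | 23.2% | 13.9% | 8.5% |
| 0.8 | 17 | 61.9% | 36.0% | 20.5% | 11.0% |
| 0.8 | 25 | 79.1% | 50.0% | 28.3% | 14.2% |
| 1.0 | 17 | 80.7% | 51.6% | 29.3% | 14.5% |
| 1.0 | 25 | 93.4% | 68.8% | 41.0% | 19.5% |

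As r approaches 0, power falls to the 5% false-positive rate.

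The half-width of a 95% CI for the difference in means, in units of the observed SD, is t × √(2/n): 2.037 × √(2/17) = 0.70 at 17 per arm and 2.011 × √(2/25) = 0.57 at 25 per arm.

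Two things follow. Lower reliability moves the result towards a null. The sample size already does much of this with a perfect scale.

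**The case against.** Four objections deserve an answer.

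**Mesh lie may be detectable.** A reader might infer that the mesh cannot be assessed at all unless it is exposed, so that the scale measures nothing. The documents do not support that. They never say that the mesh is out of reach of the examination, the anterior label speaks of how the mesh seems to lie, and the visit includes palpation for suture and anchors. Folding might be felt or show as contour. This objection stands, and it limits the point to indirect measurement by an unstated method.

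**The bias is not quantified.** A reader might also infer that the form will return no difference whatever the truth. That would need reliability near zero, and the documents give no reliability, SD or score distribution. Sample size and the absence of a margin would favour a null result on any scale. This stands too: rewording alone does not make the comparison well powered.

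**Section 5.3.ii may have merged two forms.** The instruction and the global item read as if written for an operating surgeon, and the schedule already has a surgeon and fellow satisfaction VAS at surgery. Some items may have been meant for that form. This is plausible, but the text assigns the wall VAS to the blinded examiner and introduces the four components directly afterwards. If forms were merged, the plan still has to say who completes which item and when, and it would then contain no wall-appearance item at all.

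**It is one secondary outcome.** This is true. The primary outcome is untouched, and POP-Q failure, mesh exposure or erosion, and palpable anchors are recorded separately at the same visits. That limits the weight of the point but does not repair hypothesis iii, which rests on this VAS alone.

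**Conclusion.** The point holds as a mismatch between a named outcome and its instrument. As written, all three compartment scales rate mesh lie, the fourth item rates a technique that the masked rater cannot know, and no method of judging is stated. The scale does not directly measure what hypothesis iii is about, so a null result would be weak support for no difference.

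The finding of mismatch rests on the text alone. That mesh lie is judged only indirectly is an inference from where the mesh is fixed. The loss of sensitivity is a likely direction and not an estimate; the power figures are illustrations under assumed differences and reliabilities. The trial's size and the missing margin would leave a null result uninformative for differences of several tenths of an SD even with a well-worded scale.

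This is a cheap correction worth making before the form is used. It does not threaten the primary analysis.

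**What to change.** 1. In section 5.3.ii and on the postoperative form, reword the anterior, posterior and apical end labels to what the examiner can see or feel on the vaginal wall. For example: left end, wall smooth with no fold, ridge or puckering seen or felt; right end, wall markedly folded, ridged or puckered. State that the judgement is made by inspection and palpation.
2. Assign the global technique item to the operating surgeon, at surgery, alongside the existing satisfaction VAS, and remove it from the blinded examiner's form.
3. In Protocol section 6.3 and SAP section 1.3, name the wall-appearance VAS and report the between-arm difference with a 95% CI, so that readers can see which differences remain compatible with the data. The interval methods now mentioned there are for odds ratios.

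The cost is one reworded form, one item moved to an operative form already in use, and a sentence in the analysis section. There is a small downside: the compartment scores would no longer rate mesh lie. If that is still wanted, it can be an optional item scored by the surgeon on the operative form and reported as unblinded.

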## 6. DATA MANAGEMENT AND ANALYSIS

1. PROCEDURES FOR DATA COLLECTION: Study participants will be closely observed by investigators to make sure that surgical appointments are set up. Data from preoperative period will be taken from the the EMR for the subject. Data for the primary outcome will be abstracted when the subject has their surgery.  
A Clinical report Form (CRF) will be used to collect history, physical examination, operation, operating times, technique, mesh attachment interval times, complications, and subsequent follow-up examination data. The investigators will input data into a pre-formatted spreadsheet. The spreadsheet will be maintained through the Kaiser Permanente San Diego research department on a password protected server and will be audited, reviewed and maintained by the investigators
  - i. Quality of Data: Data of the highest quality will be obtained from management data defined protocols for evaluating its accuracy (using source verification), completeness, accountability, and integrity.
  - ii. Completeness: the investigators will identify and complete any missing data.
  - iii. Accuracy: Errors in data will likely stem from errors in data entry. To minimize this, confirmation of data with a second source and random checks of data, and will be done. Error catching mechanisms in the Excel spread sheet and Access Database will be created with appropriate ranges and limits to help catch mistakes in data entry and allow for more accurate data entry.
  - iv. Auditing: Both sample and schedule-based auditing will be performed. Quarterly audits will be performed with random selection of 10% of the data to verify. Administrative audits will be done on a similar schedule to ensure compliance with Good Clinical Practices of the FDA.
  - v. Accountability: Accountability for data entry and data management will be with the investigators and statistical consultants.
  - vi. Integrity: mirrored hard drives, data back ups and storage on Kaiser Permanente San Diego server, will insure for data integrity.
2. ANALYSIS OF BASELINE DATA: Subject characteristics (measures and demographic information) collected at baseline will be compared across treatment groups, using either chi-square for categorical variables or t-test for continuous variables. We will examine these baseline characteristics for statistically significant differences between treatment groups, and use those that are identified for adjusted analysis correcting for these

differences in analysis of outcome variables.

3. **STATISTICAL ANALYSIS OF OUTCOMES:** The primary endpoint for this study is the time of completion of mesh attachment. Statistical methods will include t-test or Mann Whitney U test for continuous variables, and chi-squared or Fischer's exact-test for categorical variables. We will collect the primary measure for outcomes of time of mesh attachment as a continuous variable. In addition we will use t-tests to evaluate the mean times of the different attachment approaches. Paired sample t test will be used to evaluate POP-Q values pre and postoperatively. Chi-squared test will be used to examine anatomic failures between the two. We will do risk analysis as appropriate using 95% confidence intervals odds ratios. For the analysis we will use SPSS 22.0.
4. **STUDY POWER AND SAMPLE SIZE:** A time of mesh attachment power calculation was performed using Power and Sample Size program (PS version 3.1.2). If suture mesh attachment interval =  $40 \pm 20$  mins [16,25], a 50% reduction with use of anchors is =  $20\text{mins} \pm 20$  mins. With 80% power and  $\alpha=0.05$ , 17 subjects will be needed for each arm. Anticipating a drop out of up to a 30% we will enroll 25 subjects in each group for a goal of at least 17 participants for each arm.

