2. ANALYSIS OF BASELINE DATA: Subject characteristics (measures and demographic information) collected at baseline will be compared across treatment groups, using either chi-square for categorical variables or t-test for continuous variables. We will examine these baseline characteristics for statistically significant differences between treatment groups, and use those that are identified for adjusted analysis correcting for these differences in analysis of outcome variables.
3. STATISTICAL ANALYSIS OF OUTCOMES: The primary endpoint for this study is the time of completion of mesh attachment. Statistical methods

will include t-test or Mann Whitney U test for continuous variables, and chi-squared or Fischer's exact-test for categorical variables. We will collect the primary measure for outcomes of time of mesh attachment as a continuous variable. In addition we will use t-tests to evaluate the mean times of the different attachment approaches. Paired sample t test will be used to evaluate POP-Q values pre and postoperatively. Chi-squared test will be used to examine anatomic failures between the two. We will do risk analysis as appropriate using 95% confidence intervals odds ratios. For the analysis we will use SPSS 22.0.

4. STUDY POWER AND SAMPLE SIZE: A time of mesh attachment power calculation was performed using Power and Sample Size program (PS version 3.1.2). If suture mesh attachment interval =  $40 \pm 20$  mins [16,25], a 50% reduction with use of anchors is =  $20\text{mins} \pm 20$  mins. With 80% power and  $\alpha=0.05$ , 17 subjects will be needed for each arm. Anticipating a drop out of up to a 30% we will enroll 25 subjects in each group for a goal of at least 17 participants for each arm.

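### The only analysis that names POP-Q values is a paired pre/post t-test, which cannot compare anchors with sutures, and baseline POP-Q enters a between-arm comparison only if it happens to differ significantly at baseline

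*Protocol*

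**What the plan says.** Protocol 5.3.ii lists among the secondary efficacy items "post-operative POPQ, mesh erosion anatomic assessment, palpable anchor assessment". On timing it says "The latter two will be recorded by the provider who is blinded at 6 weeks and 6 months". The study schedule (Protocol 5.2.i) places POP-Q under efficacy at screening, 6 weeks and 6 months.

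Protocol 6.3, repeated in SAP 1.3, contains four statements that bear on this outcome:

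- For POP-Q values by name: "Paired sample t test will be used to evaluate POP-Q values pre and postoperatively". No point, visit or grouping (pooled or by arm) is given.
- For failure, which Protocol 5.3.ii defines from Ba, Bp and C: "Chi-squared test will be used to examine anatomic failures between the two".
- For effect estimates: "We will do risk analysis as appropriate using 95% confidence intervals odds ratios". Odds ratios do not apply to values in cm.
- In general: "Statistical methods will include t-test or Mann Whitney U test for continuous variables". This line is not tied to any outcome.

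On covariates, Protocol 6.2 states: "We will examine these baseline characteristics for statistically significant differences between treatment groups". SAP 1.2 continues that the investigators will "use those that are identified for adjusted analysis correcting for these differences in analysis of outcome variables". Baseline POP-Q is measured at screening, so this rule covers it. Nothing names it as a planned covariate.

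**The concern.** A paired test shows whether POP-Q improved after surgery. It can be significant in both arms even when one arm ends with poorer support, so it says nothing about the randomised comparison. The failure test shows whether more women fail in one arm, but not in which compartment or by how many cm.

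The question has some weight in this trial. The protocol's background (section 3) reports that suture gave the greatest acute fixation strength, and that absorbable anchors may carry higher recurrence in hernia repair. Its rationale is a shorter operation with similar patient outcomes. An interval for the between-arm difference would show how large a loss of support the data can exclude.

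The baseline value of the same point is the obvious covariate. Letting a significance test decide whether to use it makes the model depend on the data, and it leaves most chance imbalances uncorrected.

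**Working it through.** **The plan's own figure.** The only sample size given is for attachment time: 40 versus 20 minutes, SD 20, 80% power, α 0.05 (taken as two-sided). The standardised difference is 20/20 = 1. The noncentral t calculation gives 16.7, so 17 per arm, with 80.7% power. Then 17/0.70 = 24.3, so 25 per arm. The plan's figure reproduces. It has no bearing on POP-Q, except that 17 and 25 per arm bracket the number likely to be analysed.

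**Assumed inputs.** The documents give no POP-Q mean, SD or correlation. Assumed here: baseline mean +2 cm, SD 2; 6-month mean −2 cm with sutures, SD 1.5; pre/post correlation r from 0.1 to 0.7.

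**1. What the paired test can show.** Let anchors be 1 cm worse at 6 months (−1 cm against −2 cm). In simulation (40,000 trials per setting), the paired test is significant in both arms in at least 99.8% of trials. When the arms are equal it is significant in both in about 100%. It does not separate the two cases. At r = 0.5, a two-sample t-test rejects in about 5% of trials when the arms are equal. When anchors are 1 cm worse it rejects in 47% (17 per arm) or 64% (25 per arm). The near-certainty of the paired result depends on the assumed large improvement. For a mean improvement of only 1 cm, single-arm power is 37–77% with 17 women and 52–92% with 25.

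**2. Width of the between-arm 95% interval.**

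- Unadjusted half-width = t(0.975, 2n−2) × SD × √(2/n).
  - n = 17: 2.037 × 1.5 × 0.343 = 1.05 cm.
  - n = 25: 2.011 × 1.5 × 0.283 = 0.85 cm.
- ANCOVA half-width = t(0.975, 2n−3) × SD × √(2/n) × √(1−r²) × √(1+1/(2n−4)).

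| r | 17 per arm (cm) | 25 per arm (cm) |
|---|---|---|
| Unadjusted | 1.05 | 0.85 |
| 0.1 | 1.06 | 0.86 |
| 0.3 | 1.02 | 0.82 |
| 0.5 | 0.92 | 0.75 |
| 0.7 | 0.76 | 0.62 |

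At r = 0.5 the ratio to the unadjusted width is 0.92/1.05 = 0.88 and 0.75/0.85 = 0.88, so about 12% narrower. At r = 0.1 there is no gain. If the SD is 1.0 to 2.0 cm instead, the unadjusted half-width is 0.70–1.40 cm (17 per arm) or 0.57–1.14 cm (25 per arm).

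**3. What the baseline screen lets through.** Under randomisation, a 5% test is significant in about 5% of trials per point, so baseline is left out in about 95%. The largest non-significant imbalance is t(0.975, 2n−2) × 2 × √(2/n):

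- n = 17: 2.037 × 2 × 0.343 = 1.40 cm.
- n = 25: 2.011 × 2 × 0.283 = 1.14 cm.

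Left unadjusted, such an imbalance shifts the expected 6-month difference by r × (1.5/2) × imbalance. At r = 0.5 this is 0.5 × 0.75 × 1.40 = 0.52 cm, or 0.5 × 0.75 × 1.14 = 0.43 cm. At r = 0.1 it is 0.10 or 0.09 cm; at r = 0.7 it is 0.73 or 0.60 cm. These are upper limits for a non-significant imbalance, not typical values.

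**The case against.** The strongest reply is that the plan's stated POP-Q question already has its comparison. The secondary objective is POP-Q evaluation for anatomic failure, the hypothesis is similar failure rates, and failure is tested between arms. No objective or hypothesis concerns POP-Q in cm. This stands, and it limits the point to the values themselves, which Protocol 5.3.ii does list as an outcome.

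A reader might infer that the arms will never be compared on POP-Q values. The documents do not support that. The general line on t-tests and Mann-Whitney tests can reasonably be read to cover them, and a two-sample t-test supplies a mean difference and interval. But the line names no point, visit, estimate or covariate, and the same paragraph then assigns POP-Q the paired test.

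A reader might also infer that the paired test is meant to show anchors equal to sutures. Nothing in the plan says so; it is described only as a pre/post evaluation.

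Nor is the unadjusted comparison invalid. In simulation its type I error was 4.8–5.1%, and the shifts in step 3 are conditional on an imbalance, not a bias over repeated randomisation. Adjustment is about precision and protection from chance imbalance.

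Finally, it would be tempting to test C alone because apical descent is an entry finding. That is poorly grounded. The arms differ in how mesh is attached to the anterior and posterior vagina, Ba and Bp are entry and failure points too, and failure at C is defined relative to vaginal length.

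**Conclusion.** The point holds, at modest size, for a secondary outcome. It rests on the text of both documents: the one analysis that names POP-Q values has no arm contrast, and the covariate rule leaves baseline POP-Q out in about 95% of randomised trials per point.

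The numerical gain from planned adjustment rests wholly on assumed inputs. It ranges from nothing at r = 0.1, through about 12% at r = 0.5, to about 27% at r = 0.7 with 17 per arm (0.76/1.05 = 0.73). Even then the interval is wide, roughly ±0.6 to ±1.1 cm at an SD of 1.5 cm, so it cannot carry a claim of equivalence.

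No power advantage over the failure test is claimed. The primary analysis and the sample size are unaffected. The change is worth making because it costs almost nothing and answers a question the paired test cannot.

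**What to change.** In Protocol 6.3 and SAP 1.3, replace the paired-test sentence with:

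> 6-month Ba, Bp and C will each be compared between arms by ANCOVA with the baseline value of the same point as covariate, whatever the baseline comparison shows, and reported as adjusted mean differences (anchor minus suture) with 95% CI, as supportive estimates without a claim of equivalence. 6-week values are reported in the same way. Within-arm pre/post changes are descriptive.

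Keep the chi-squared or Fisher comparison of anatomic failure as the test of the failure hypothesis. No single POP-Q point needs to be singled out for testing. Because the three points are reported as estimates, no multiplicity correction is needed.

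The cost is wording in two documents. POP-Q is already scheduled at all three visits, so no data collection is added. Women lost to follow-up (the plan anticipates up to 30%) will be missing from this analysis, as they are from the POP-Q and failure analyses already planned.
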